5.4.2. Safety Analysis Set

The Safety Analysis Set (SAS) will consist of all randomized patients who received at least one dose or portion of a dose of study drug.

5.4.3. Pharmacokinetics Analysis Set

The Pharmacokinetics Analysis Set (PKS) will consist of all randomized patients who have at least one evaluable plasma concentration of reldesemtiv, provided they have no major protocol violations that could affect the PK results of reldesemtiv.

5.4.4. Use of Analysis Sets in Different Analyses and Summary Level

The analysis datasets to be used are described in [Table 2](#).

Table 2: Analysis Set and Summary Level

Analyses	Analysis Set
Patients Disposition (Section 6.1)	Randomized Patients, FAS
Study Population (Section 6) except for Patients Disposition (Section 6.1) and Screen Failures (Section 6.2)	SAS, FAS
Efficacy Analyses (Section 7)	FAS
Safety and Tolerability (Section 8)	SAS
PK/PD Analyses (Section 9)	PKS

5.5. Definitions

5.5.1. Baseline Assessments

Baseline assessments are defined as the last non-missing measurement prior to administration of the first dose of study drug.

5.5.2. Change from Baseline

Change from baseline is calculated as (post baseline result – baseline result).

Percent change from baseline is calculated as (change from baseline/baseline result) x 100%.

If either the baseline or the post baseline result is missing, the change from baseline and/or percentage change from baseline will be set to missing.

5.5.3. Study Day

If the date of interest occurs on or after the first dose date, then study day will be calculated as (date of interest – date of first dose) + 1. If the date of interest occurs prior to the first dose date, then study day will be calculated as (date of interest – date of first dose). There is no study day 0.

5.5.4. Analysis Visit Windows

Since study visits do not always take place exactly as scheduled in the protocol, it is necessary to assign the actual observation dates to visit windows for analysis purposes.

For measurement taken prior to the first dose of study treatment, the visit window is defined as the interval of time prior to the first dose of study treatment. Measurements taken on or after the first dose of study treatment will be assigned to the next scheduled visit window.

For data collected at a scheduled post baseline visit, the visit window is assigned based on the scheduled study day of the nominal visit as collected on the electronic case report form (eCRF).

For unscheduled or early discontinuation post baseline visits, measurements taken on or after the first dose of study treatment will be assigned to a visit window using defined lower and upper bounds for each visit window. Measurements assigned in a visit window will have study day greater than or equal to the lower bound but no greater than the upper bound of the visit window. The lower bound and the upper bound for the visit windows are defined as the midpoints of the scheduled visits for all assessments (see [Appendix B](#)).

Visits are identified as the nominal visits according to the eCRFs. Each visit will be identified with the visit descriptor (eg, “Week 12”). If a patient has two or more study visits in one visit window, one record will be flagged as the “analyzed record” for that visit window.

5.5.5. Determining “Analyzed Record” for Each Analysis Visit Window

Once visit windows are assigned, a patient’s individual visit window could potentially contain more than one visit. Records from all visits, including scheduled, unscheduled and early discontinuation visits could be flagged as the “analyzed record” within the visit window, although the records from scheduled visit will take priority.

For measurement taken prior to the first dose of study treatment, in the event of multiple visits falling within the visit window, the following rule will be used to determine the “analyzed record”:

- The record closest to, but prior to the first dose of study treatment should be selected as the baseline “analyzed record.” This could include scheduled visits and other screening visits.

For post baseline visits, in the event of multiple visits falling within a visit window, the following rules will be used in sequence to determine the “analyzed record” for the visit window:

- If a scheduled visit occurred during the visit window, then the measurement taken from the scheduled visit will be used.

- If no scheduled visit occurred during the visit window, the measurement taken closest to the scheduled day will be used as the “analyzed record.”
- If no scheduled visit occurred during the visit window and there is a tie between visits in the number of days before and after the scheduled day, measurements from the later visit will be used as the “analyzed record.”

For all analyses, only the “analyzed record” within each visit window will be summarized in a table. If there are other visit records within the visit window, they will only be included in data listings. In addition, composite scores (eg, ALSFRS-R total score or muscle strength mega score) will be calculated based on the “analyzed record.”

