5.8. Early Termination Visit

If a patient decides to terminate early from the study, they should be seen in the clinic as soon as possible following discontinuation of study drug. The following procedures will be performed:

1. 12-lead ECG
2. Vital signs including heart rate, blood pressure, and respiratory rate measured after the patient has been resting for at least 3 minutes
3. Weight
4. Abbreviated physical examination
5. Neurological examination
6. Clinical laboratory evaluations, including CBC and WBC with differential, serum chemistries, cystatin C and UA

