8.4. Routine Laboratory Data

Clinical laboratory evaluations, including hematology, serum chemistry, and urinalysis as detailed in the protocol, will be collected at the Screening, Day 1, Week 2, Week 4, Week 12 and Follow-Up Visits. Descriptive statistics of assessment value and change from baseline of laboratory parameters will be presented at each assessment time point by dose level and overall.

The number and percentage of patients who had normal or missing laboratory values at baseline and abnormal laboratory values post baseline will be presented by dose level and overall. The lower limit of normal (LLN) and upper limit of normal (ULN) provided by the laboratories will be used as the criteria for abnormality. For each parameter, the denominator of the percentage will include patients with normal or missing assessments at baseline, and with at least one assessment post baseline. The numerator of the percentage will include patients who had at least one abnormal assessment post baseline among the patients that were counted in the denominator. Assessment collected at an unscheduled visit or the Follow-up Visit will also be included in the summary.

Shift of clinical laboratory results in NCI-CTCAE grade from baseline grade to the maximum post baseline grade will be presented for selected laboratory parameters. Clinical laboratory values will be also listed. Values outside the Laboratory's normal ranges and potentially clinically significant abnormal values will be flagged.

Hy's law ([Temple 2006](#)) will be used to evaluate drug induced liver injury (DILI); patients with ALT or AST elevations $> 3 \times$ ULN and total bilirubin elevations $> 2 \times$ ULN will be marked on a scatter plot. Elevations of ALT or AST to $5 \times$, $10 \times$ or $20 \times$ ULN will also be plotted.

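### SAP 5.5.5 applies its one-record-per-window rule to all analyses, which conflicts with the worst-value safety outputs in 8.4 to 8.6 and leaves early termination and unscheduled values unsettled

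*SAP*

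**What the plan says.** SAP 5.5.4 maps off-schedule visits into analysis windows by study day: "For unscheduled or early discontinuation post baseline visits, measurements taken on or after the first dose of study treatment will be assigned to a visit" (the sentence goes on to the day bounds). It names early discontinuation visits separately from unscheduled ones. The bounds are in Appendix B.

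SAP 5.5.5 then picks one record per window. The priority rule is: "If a scheduled visit occurred during the visit window, then the measurement taken from the scheduled visit will be used". The scope is: "For all analyses, only the “analyzed record” within each visit window will be summarized in a table". Everything else is covered by: "If there are other visit records within the visit window, they will only be included in data listings".

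The safety sections are worded differently. SAP 8.4 (labs), 8.5 (vital signs) and 8.6 (ECG) count patients with at least one abnormal or PCS value after baseline, and each adds: "Assessment collected at an unscheduled visit or the Follow-up Visit will also be included in the summary". SAP 8.4 also plans a "Shift of clinical laboratory results in NCI-CTCAE grade from baseline grade to the maximum post baseline grade", a Hy's law scatter plot, and summaries and a time-to-event analysis of eGFR decline. None of these last outputs says which records it uses.

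Protocol 8.4.5.4 to 8.4.5.6 count lab, vital sign and ECG abnormalities over the whole study. SAP Section 12 lists no departure from the protocol. Protocol 5.8 requires an ECG, vital signs and labs at the Early Termination visit, the labs being: "Clinical laboratory evaluations, including CBC and WBC with differential, serum chemistries, cystatin C and UA".

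**The concern.** A one-record rule suits means by visit. It does not suit an output meant to show a patient's worst value, because the record it sets aside may be the worst one. An early termination visit comes just after a patient stops drug. Protocol 5.15 lists an eGFR decline of more than 25% and liver test changes among the possible reasons for stopping.

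The schedule is also sparse. No labs are planned between Week 4 and Week 12, and the only planned post-baseline ECGs are at Week 4 and Follow-Up. Under protocol 5.15, patients who stop drug return for remaining visits without labs or ECG until Follow-Up, 28 days after the last dose. For someone who stops between Weeks 4 and 12, the early termination labs and ECG are the only ones the visit schedule provides between Week 4 and Follow-Up. Protocol 1.3 describes reversible creatinine rises, so a later sample need not show the same picture.

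At stake is whether programmers keep these records in the liver, renal and grade-shift outputs. As written, two careful programmers could produce different tables.

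**Working it through.** **Inputs.** Scheduled days (protocol Table 2, SAP Appendix B): Weeks 2, 4, 8 and 12 are Days 15, 29, 57 and 85; Follow-up is Day 113. Labs are scheduled at Weeks 2, 4, 12 and Follow-up, ECG at Week 4 and Follow-up, and vital signs at every visit (Appendix A of both documents).

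**Step 1: reproduce the window bounds.** SAP 5.5.4 says: "The lower bound and the upper bound for the visit windows are defined as the midpoints of the scheduled visits for all assessments". So lower bound = (a + b)/2 for consecutive scheduled days a and b.
- Labs: (15+29)/2 = 22; (29+85)/2 = 57; (85+113)/2 = 99.
- ECG: (29+113)/2 = 71.
- Vital signs: 22; (29+57)/2 = 43; (57+85)/2 = 71; 99.

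All match Appendix B.

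**Step 2: count the days on which an earlier scheduled record displaces an early termination record.** Possible days are 2 to 84, that is 84 − 2 + 1 = 83. Assume each scheduled visit was held on its nominal day.
- Labs: Week 2 window 2–21, visit Day 15, gives Days 16–21 (6 days). Week 4 window 22–56, visit Day 29, gives Days 30–56 (27 days). Total 33; 33/83 = 39.8%. From Day 57 the record falls in the Week 12 window, where an off-drug patient is not due labs, so it becomes the analyzed record.
- ECG: Week 4 window 1–70, visit Day 29, gives Days 30–70 (41 days); 41/83 = 49.4%. Days 71–84 (14 days) fall in the Follow-up window, where the scheduled Follow-Up ECG would take priority if it is done. That is displacement by a later visit, so it is kept separate.
- Vital signs: Days 16–21, 30–42 and 58–70, or 6 + 13 + 13 = 32; 32/83 = 38.6%. Vital signs continue at later visits for patients who return.

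Unscheduled labs are more exposed. The lab windows run without a gap from Day 2, so a patient who attends every scheduled lab visit has a scheduled record in every window, and that record always wins.

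**Step 3: set the outputs against the rule.**

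| Output | Its own record rule | Effect if 5.5.5 is followed literally |
|---|---|---|
| By-visit summaries (8.4–8.6) | One value per time point | Displacement intended and defensible |
| Any-abnormality and PCS tables (8.4–8.6) | At least one post-baseline value; unscheduled and Follow-up added | Unscheduled kept; early termination not named, so ambiguous |
| CTCAE shift (8.4) | Maximum grade, with the set of records not stated | Displaced values left out |
| Hy's law plot (8.4) | None | Displaced values left out |
| eGFR decline summaries and time-to-event (8.4) | None | Displaced values left out |

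**The case against.** A reader might infer that abnormalities found when a patient stops drug disappear from the safety tables. The documents do not support that. The any-abnormality and PCS tables count any qualifying post-baseline value and expressly add unscheduled and Follow-up records. Early termination is not one of the seven study visits in protocol 3.1 and has no column in the schedule of events, so reading it as unscheduled is reasonable. The protocol counts abnormalities at any time in the study. Clinically significant changes are reportable as adverse events, events leading to discontinuation are tabulated (SAP 8.1.2), and displaced values stay in listings with out-of-range labs and PCS ECGs flagged. All of this stands.

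Three further arguments hold only in part.
- A maximum grade looks like a worst-value rule by its own terms. But a maximum taken over analyzed records alone is also coherent, and 5.5.5 claims all analyses.
- The Hy's law output is a plot, while one 5.5.5 sentence speaks of tables. The next sentence sends other records only to listings, and a plot is not a listing.
- Protocol Appendix C requires repeat tests after an ALT or AST above 3 × ULN. Those repeats are unscheduled records, which 8.4 adds to the abnormality table. It does not add them to the shift or the plot.

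A reader might also multiply the day fractions by the planned dropout (10% of 445 = 44.5), which gives about 18 lab sets (0.398 × 44.5) and 22 ECGs (0.494 × 44.5). The documents do not support that as a count of losses. They give no distribution of stopping times, protocol 5.8 allows a phone contact with no labs or ECG, and displaced records may be entirely normal.

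**Conclusion.** The conflict is real and minor. SAP 5.5.5 is broader than the safety sections and the protocol allow. Followed literally, it leaves early termination and unscheduled values that share a window with a scheduled visit out of the CTCAE maximum-grade shift, the Hy's law plot and the eGFR decline analyses, which carry no exception. For the any-abnormality and PCS tables, early termination records are ambiguous rather than excluded.

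The opportunity for displacement by an earlier scheduled visit is 33 of 83 days for labs and 41 of 83 for ECG, with a further 14 ECG days in the Follow-up window. This assumes scheduled visits on their nominal days and an in-clinic early termination visit on Days 2 to 84. How many abnormal values would be affected cannot be estimated from the documents, and no loss of a safety signal has been shown.

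**What to change.** 1. In SAP 5.5.5, limit the one-record rule to by-visit summaries and models.
2. State there that the any-abnormality and PCS tables, the CTCAE maximum-grade shifts, the Hy's law plot, and the eGFR decline summaries and time-to-event analysis use all post-baseline records, including early termination and unscheduled visits.
3. Add early termination visits to the inclusion sentence in SAP 8.4, 8.5 and 8.6.

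The cost is a few lines of SAP text and the matching programming before database lock. No new data are needed, and by-visit summaries and efficacy models are unchanged.

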5.5.6. Pooled Sites

The “study site” will be used as a fixed effect in the efficacy analysis models. For analysis purpose, study sites that have few patients enrolled (eg, less than 10% of patients among all enrolled) may be pooled to ensure sufficient number of patients from each site and approximately equal number of patients among the sites. For study sites with few patients enrolled, the sites within a country will be pooled by geographic proximity into groups with appropriate number of patients in each group. If an entire country has less patients enrolled compared to other study sites, all sites within the country will be pooled into one group, and the group will further be pooled across countries as appropriate. See [Appendix C](#) for regional site pooling for FAS.

5.5.7. Calculated Rate of Pre-Study Disease Progression

Change in ALSFRS-R total score will be used to represent the status of ALS disease progression. The pre-study rate of disease progression evaluated at baseline will be calculated as the change in ALSFRS-R total score between the date of ALS symptom onset and the date at baseline. Assuming a patient has a ALSFRS-R total score of 48 at the time of ALS symptom onset, the rate of disease progression per month evaluated at baseline can be calculated as follows: $(48 - \text{ALSFRS-R total score at baseline}) / \text{months (30.25 days) since ALS symptom onset}$.

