8.1.2. Sample Size and Randomization

Approximately 445 patients will be randomized to receive either one of the three CK-2127107 doses (300 mg/day, 600 mg/day and 900 mg/day TDD) or matching placebo tablets in a ratio of 1:1:1:1. Randomization will be stratified by riluzole use/non-use and edaravone use/non-use. The dropout rate at Visit Week 12 is estimated to be 10%, thus approximately 400 patients are expected to complete 12 weeks of double-blind treatment. The effect of CK-2127107 on the change from baseline to Week 12 in percent predicted SVC will be analyzed using a mixed model for repeated measures (MMRM) with the contrast (-5, -1, 3, 3) to reflect the assumed relationship for the placebo, 300 mg/day, 600 mg/day and 900 mg/day dose groups. The analysis is estimated to provide 90% power to detect 2.75, 5.5 and 5.5 percentage points advantage over placebo for the 300 mg/day, 600 mg/day and 900 mg/day CK-2127107 dose groups, respectively, in change from baseline of percent predicted SVC, at the end of the double-blind treatment (Visit Week 12). This calculation is based on a two-sided test with alpha set at 0.05 and a common standard deviation of 14 percentage points.

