7.5. Analysis of the Primary Efficacy Endpoints

7.5.1. Primary Efficacy Analysis

The primary efficacy endpoint (change from baseline to Visit Week 12 in percent predicted SVC) will be analyzed for the FAS based on the percent predicted SVCs collected in clinic and were confirmed evaluable by the central read of an independent pulmonologist. A MMRM with the contrast (-5, -1, 3, 3) will be used for the analysis to reflect the assumed relationship for the placebo, 300 mg/day, 600 mg/day and 900 mg/day dose groups. The response variable will be the change from baseline to each post baseline visit up to Week 12. The model will include the following covariates:

- Treatment (reldesemtiv 300 mg/day, 600 mg/day and 900 mg/day, and placebo)
- Baseline (baseline value of the response variable)
- Pooled site (Center)
- Visit (scheduled, a categorical variable)
- Riluzole and edaravone use status at baseline
- Treatment-by-visit interaction
- Baseline-by-visit interaction

An unstructured variance-covariance structure will be used to model the within-subject errors. If a model fails to converge, other covariance matrix structures (eg, compound symmetry) may be used instead of the unstructured covariance matrix. Least square means and the corresponding standard errors, 95% CIs and p-values will be presented.

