7.9. Exploratory Analyses

7.9.1. Joint Rank Test

Joint rank analyses using the combined assessment of function and survival (CAFS) ([Berry 2013](#)) will be conducted to account for survival time in the analyses of change in the percent predicted SVC and ALSFRS-R total score at Week 12, individually.

Each patient will be compared with all others in the analysis population in a pairwise manner on their survival status and the functional measurements, ie, changes from baseline in the percent predicted SVC or ALSFRS-R total score. A score of +1 or -1 will be assigned if one has better or worse outcome than the other, respectively. The following rule will be used:

- Patients who died are ranked worse than those who survived.
- Among patients who died, patients who died first are ranked worse.
- For patients who discontinued treatment early but were alive, comparison is based on the last time-point measurements that are both available for the patients in pairs. A patient is ranked worse if the patient discontinued treatment early and did not have functional measurement collected before the discontinuation.
- Among patients who completed, patients with greater decline from baseline in the functional measurement are ranked worse.
- If it is not possible to assign either patient as having the better outcome, then the score assigned to the pair is 0.

For each patient, the assigned scores from the pairwise comparisons with all others will first be summed, and all patients in the analysis population will be ranked according to their summated scores to create a rank score from 1 for the lowest summated score to N (total number of patients in the analysis population) for the highest summated score. If ties occur, each of the tied summated scores will be assigned the average of the ranks the tied summated scores would have if there were no ties.

The rank scores will be analyzed using the generalized Gehan-Wilcoxon test. In addition, the rank scores will be analyzed using an ANCOVA model that adjusts for baseline variables (baseline functional measurement, time from symptom onset, site of disease onset and riluzole or edaravone use). The rank scores between the reldesemtiv and placebo groups will be compared, and the least square mean difference as well as the p-value will be presented.

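### The primary MMRM does not adjust for the pre-study progression rate that the SAP already derives: forgone precision of unknown size, not an error or a power shortfall

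*SAP*

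**What the plan says.** SAP 5.5.7: "The pre-study rate of disease progression evaluated at baseline will be calculated". The formula is 48 minus the baseline ALSFRS-R total, divided by months since symptom onset. The only stated use of the result is the tertile subgroup in SAP 7.3.

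The covariates of the primary MMRM agree across Protocol 8.4.4.1, SAP 7.5.1 and the first SAS prototype in SAP Section 13. They are treatment, visit, pooled site, riluzole and edaravone use, one baseline term, and the treatment-by-visit and baseline-by-visit interactions. SAP 7.5.1 describes the baseline term as "Baseline (baseline value of the response variable)". The ALSFRS-R model is the same apart from the response (SAP 7.6). The mega-score slope model in SAP 7.6 has no baseline prognostic term other than background drug use and site.

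SVC is measured at both Screening and Day 1 (Protocol 5.1, 5.2 and Appendix A). SAP 5.5.1 keeps one value: "Baseline assessments are defined as the last non-missing measurement prior to administration of the first dose of study drug". Screening SVC therefore enters only when there is no usable Day 1 value.

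For the exploratory joint-rank analysis of SVC and ALSFRS-R, SAP 7.9.1 adjusts for "baseline functional measurement, time from symptom onset, site of disease onset and riluzole or edaravone use".

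**The concern.** The endpoint is decline over 12 weeks, and how fast a patient declined before entry is a plausible predictor of it. Randomization is stratified only by riluzole and edaravone use, and the eligibility criteria do not limit progression rate. A chance imbalance in fast progressors is therefore handled neither by the design nor by the model. The SAP adjusts an exploratory analysis of the same two outcomes for disease history, but not the primary one.

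At stake is the width of the confidence interval for the primary contrast, and for the two endpoints tested after it (SAP 7.4). A pre-specified pre-dose covariate leaves the estimand unchanged and shortens the interval to the extent that it explains residual variance.

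**Working it through.** **Inputs (Protocol 8.1.2).** "mixed model for repeated measures (MMRM) with the contrast (-5, -1, 3, 3)"; "The analysis is estimated to provide 90% power to detect 2.75, 5.5 and 5.5 percentage points advantage over placebo" for 300, 600 and 900 mg/day; "matching placebo tablets in a ratio of 1:1:1:1"; "This calculation is based on a two-sided test with alpha set at 0.05 and a common standard deviation of 14 percentage points". About 445 are randomized, with 10% dropout and about 400 completers, so 100 per arm.

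**The plan's own figure.**
- Contrast: −5×0 − 1×2.75 + 3×5.5 + 3×5.5 = 30.25.
- Sum of squared coefficients: 25 + 1 + 9 + 9 = 44.
- SE = 14 × √(44/100) = 9.29.
- z = 30.25/9.29 = 3.257. Power = Φ(3.257 − 1.960) = 90.3% (noncentral t: 90.1%).
- n per arm for 90%: 44 × [14 × (1.960 + 1.282)/30.25]² = 99.03, rounded up to 100. That is 400 completers, and 400/0.9 gives 445 randomized.

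The stated power and sample size reproduce with no additional covariate.

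**Adding the progression rate.** Let R² be the share of residual variance that the rate explains beyond the planned terms. The documents do not give it, so the values below are assumptions, and 14 is treated as the residual SD under the planned model. The SD becomes 14 × √(1 − R²).

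| Assumed R² | SD | SE ratio | Power, 100 per arm | Randomized for 90% |
|---|---|---|---|---|
| 0 | 14.00 | 1.000 | 90.3% | 445 |
| 0.01 | 13.93 | 0.995 | 90.6% | 440 |
| 0.02 | 13.86 | 0.990 | 90.8% | 436 |
| 0.05 | 13.65 | 0.975 | 91.7% | 423 |
| 0.10 | 13.28 | 0.949 | 93.0% | 400 |

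SAP Section 13 divides the contrast by 6. On that scale the SE is 9.29/6 = 1.55 points and the 95% half-width is 1.96 × 1.548 = 3.03 points. R² of 0.05 or 0.10 would bring it to about 2.96 or 2.88.

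**Adding Screening SVC beside Day 1 SVC.** Assume a between-patient SD of 12 to 20 points, a visit-to-visit error SD of 3 to 7, a change SD of 14, and true change unrelated to true level. None of these except the 14 is in the documents. The second reading helps only by showing how much of the Day 1 value is noise. Example with SDs 16 and 5:
- Variance of the change given Day 1 alone: 196 − 5⁴/(16² + 5²) = 196 − 625/281 = 193.8.
- Given both readings: 196 − 625 × 281/(281² − 256²) = 182.9.
- Partial R² = 1 − 182.9/193.8 = 0.056.

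Over the whole grid, partial R² runs from about 0.02 to 0.11, and power for this addition alone from about 90.9% to 93.2%. This range and the one for the rate must not be added together.

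**The case against.** The strongest reply is that nothing is broken. Protocol, SAP and code agree on the covariates, and the trial has its stated power without more. The FAS counts in SAP Appendix C sum to 458, above the planned 445; 10% dropout from 458 leaves about 103 per arm and 91.1% power. A reader might infer that the trial is underpowered, and the figures contradict that. If 14 is an unadjusted SD, which the documents do not settle, baseline adjustment already adds margin. All of this stands.

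A reader might also take SAP 7.9.1 as the sponsor's acceptance that the progression rate is prognostic. The documents do not support that. The list there has time from onset, which is the denominator of the rate, and site of onset, but neither the rate itself nor a second pre-dose SVC. No section links the rate to 12-week SVC change. The rate also measures global function: only 3 of the 12 ALSFRS-R items are respiratory (SAP 5.5.8.2). Its partial R² for SVC change could be near zero.

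For ALSFRS-R the rate overlaps with the baseline score already in the model, so it mainly adds time since onset. That limits the gain there without removing it.

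Nor is the change free of risk. SAP 5.6.3 leaves partial onset dates unimputed, so the rate may be coarse or missing. SAP 5.5.8.1 excludes SVC readings that the central read does not confirm, so a Screening value may be missing. PROC MIXED drops records with a missing covariate. Without a rule, the addition could remove FAS patients from the primary analysis. This objection is right, and the fix must deal with it.

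**Conclusion.** The primary model omits a pre-dose variable that the SAP already derives and that plausibly predicts the outcome. Adding it would be an inexpensive gain in precision. It would not correct an error, and 90% power does not depend on it.

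The size is unknown. For an assumed partial R² of 1% to 10%, power rises from 90.3% to between 90.6% and 93.0%, and the SE falls by 0.5% to 5%. This rests on 14 being the residual SD, 100 completers per arm, and no patients lost through missing covariates. Screening SVC is secondary: it only refines a baseline term already in the model, it already serves as the fallback baseline, and its benefit is confined to reduced measurement noise. The wording that the documents support is to consider pre-specifying these terms, with the gain stated as unknown.

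**What to change.** Before database lock:

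- In SAP 7.5.1, and in the ALSFRS-R model of SAP 7.6, add the pre-study progression rate and its interaction with visit.
- In the mega-score slope model of SAP 7.6, add the rate and its interaction with time.
- Optionally, in the primary model only, add Screening percent predicted SVC beside the Day 1 baseline. Leave the definition of change from baseline as it is, and say what is done when the Screening value is itself the baseline.
- State a missing-covariate rule, for example single imputation of the covariate from pooled baseline data, blind to arm, so that every FAS patient stays in the model.
- Use one month length. SAP 5.5.7 divides by 30.25 days and SAP 5.6.3 by 30.4375. A common scale factor does not affect power, but the definitions should match.
- Update the SAS prototypes in SAP Section 13, and record the departure from Protocol 8.4.4.1 in SAP Section 12. Protocol 8.7 then requires it in the study report.

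The cost is SAP text, a few model terms with a minor loss of degrees of freedom at about 400 patients, and an imputation rule for partial onset dates or unusable Screening SVC. No new data and no patient burden are involved. The main drawback is that the gain may prove small.
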